4.5 MISSED EVALUATIONS

Missed evaluations should be rescheduled and performed as close to the original scheduled date as possible. An exception is made when rescheduling becomes, in the

Protocol: ACE-LY-001

investigator's opinion, medically unnecessary or unsafe because it is too close in time to the next scheduled evaluation. In that case, the missed evaluation should be abandoned.

5.0 STATISTICAL METHODS OF ANALYSIS

5.1 GENERAL CONSIDERATIONS

Descriptive statistics (including means, standard deviations, and medians for continuous variables and proportions and confidence intervals (Cis) for discrete variables) will be used to summarize data as appropriate. As appropriate, analyses will be performed by dosing cohort, cancer type, or overall. Depending on dose escalation into subsequent cohorts and potential expansion cohorts, up to 108 evaluable subjects will be enrolled in this study.

In Part 1 (dose-escalation portion), enrollment of 6 subjects per cohort of the study limits the total cohort size consistent with the expected safety profiles of the study drugs but includes sufficient subjects per cohort to explore dose-dependent effects on PD biomarkers of BTK and PI3Kδ inhibition. The study employs the standard National Cancer Institute definition of MTD (starting dose associated with Cycle 1 DLT in <33.3% of subjects). The cohort size and dose-escalation rules establish a low probability of increasing the dose if the true rate of DLT is high while there is a high likelihood of escalating or proceeding to the next stage of the study if the true underlying proportion of DLT is low.

In Part 2 (expansion groups), enrollment of up to 12 subjects per histology offers the opportunity to determine if there is sufficient antitumor activity to warrant further development in the selected tumor types. Considering the planned expansion cohort size of 12 subjects, Table 5-1 shows the 2-sided exact 90% binomial CIs on the true response rate for the range of all possible values for the observed response rate.

Protocol: ACE-LY-001

Table 5-1. Two-Sided Exact 90% CIs for ORR in Expansion Cohorts (N=12)

| Decrees a | Doonanaa Dota (/ | 90% Exact I | Binomial CI |
|--------------|------------------|-------------|-------------|
| Responses, n | Response Rate, % | Lower Bound | Upper Bound |
| 0 | 0% | 0% | 22% |
| 1 | 8% | 0% | 34% |
| 2 | 17% | 3% | 44% |
| 3 | 25% | 7% | 53% |
| 4 | 33% | 12% | 61% |
| 5 | 42% | 18% | 68% |
| 6 | 50% | 25% | 75% |
| 7 | 58% | 32% | 82% |
| 8 | 67% | 39% | 88% |
| 9 | 75% | 47% | 93% |
| 10 | 83% | 56% | 97% |
| 11 | 92% | 66% | 100% |
| 12 | 100% | 78% | 100% |

Abbreviations: CI=confidence interval, ORR = overall response rate

5.2 DEFINITION OF ANALYSIS POPULATIONS

The following definitions will be used for the efficacy and safety analysis populations.

All-treated population: All enrolled subjects who receive ≥1 dose of study drug. The safety analyses and primary efficacy analyses will be performed on the All-treated population.

Efficacy-evaluable population: All subjects in the All-treated population who have ≥1 evaluable response assessment after the first dose of study drug. Sensitivity analyses for efficacy will be carried out on the Efficacy-evaluable population.

5.3 MISSING DATA HANDLING

General Considerations: Subjects lost to follow-up (or who dropped out) will be included in statistical analyses up to the point of their last evaluation.

Duration of Response and Progression-free Survival: Data for subjects without disease progression or death will be censored at the date of the last tumor assessment and before the initiation of alternative anticancer therapy.

Safety: Missing or partial start and end dates for AEs and concomitant medications will be imputed according to prespecified, conservative imputation rules. No other imputation of values for missing data will be performed.

5.4 ENDPOINT DATA ANALYSIS

5.4.1 Safety Endpoint

Safety summaries will include summaries in the form of tables and listings. The frequency (number and percentage) of treatment emergent AEs will be reported in each treatment group by MedDRA System Organ Class and Preferred Term. Summaries will

Protocol: ACE-LY-001

also be presented by the severity of the AE (per CTCAE, v4.03 or higher, and by relationship to study drug (e.g., either acalabrutinib, ACP-319, or both).

Laboratory shift tables containing counts and percentages will be prepared by treatment assignment, laboratory parameter, and time. Summary tables will be prepared for each laboratory parameter. Figures of changes in laboratory parameters over time will be generated.

Results of vital sign assessments, ECGs, and physical examinations will be tabulated and summarized.

5.4.2 Demographics and Baseline Characteristics

Additional analyses will include summaries of subject demographics, baseline characteristics, and concurrent treatments. Concomitant medications will be coded and tabulated according to the WHO Drug Dictionary.

5.4.3 Study Treatment Administration

Descriptive information will be provided regarding the duration of study treatment exposure, average daily dose, and relative dose intensity.

For each subject, acalabrutinib relative dose intensity will be described in terms of the proportion of study drug actually taken relative to the amount that was planned during the treatment exposure period.

Descriptive information will be provided regarding the duration of study treatment exposure, average daily dose, and relative dose intensity.

For each subject, acalabrutinib and ACP-319 relative dose intensity will be described in terms of the proportion of study drug actually taken relative to the amount that was planned during the treatment exposure period.

5.4.4 Analysis of Efficacy Parameters

Response Rate

The primary efficacy endpoint is the ORR as assessed by investigators. ORR is defined as the proportion of subjects who achieve a response (see Table 4-4, Table 4-5, Table 4-6, Table 4-7, and Table 4-8). ORR will be calculated and the corresponding 2-sided 95% CI will be derived.

In addition, for subjects with CLL/SLL, response will be assessed according to Table 4-5, which reflects modified International Working Group response criteria (Hallek et al. 2008)

Protocol: ACE-LY-001

as recently updated (Cheson et al. 2012) to include partial remission (response) with treatment-induced lymphocytosis (PRL). For purposes of this analysis, lymphocytosis at a given timepoint will be defined as ALC, which is above normal limits and is not ≥50% decreased from baseline.

Duration of Response

The duration of response defined as the interval from the first documentation of response to the earlier of the first documentation of definitive disease progression or death from any cause. Kaplan-Meier methods will be used to estimate event-free curves and corresponding quantiles (including the median). Data from surviving, non-progressing subjects will be censored at the earliest of the time of initiation of anticancer treatment other than the study treatment or the last time that lack of disease progression was objectively documented. Data from subjects who have disease progression or die after ≥2 consecutive missing tumor assessments will be censored at the last time before the missing assessments that lack of disease progression was objectively documented.

Progression-Free Survival

Progression-free survival is defined as the interval from the start of acalabrutinib and ACP-319 therapy to the earlier of the first documentation of objective disease progression or death from any cause. Kaplan-Meier methods will be used to estimate the event-free curves and corresponding quantiles (including the median). Data from surviving, non-progressing subjects will be censored at the earliest of the time of initiation of anticancer treatment other than the study treatment or the last time that lack of disease progression was objectively documented. Data from subjects who have disease progression or die after ≥2 consecutive missing tumor assessments will be censored at the last time prior to the missing assessments that lack of disease progression was objectively documented.

Time-to-Next Treatment

Time-to-next treatment defined as the time from start of acalabrutinib and ACP-319 therapy on this protocol to the start of the next treatment. Kaplan-Meier methods will be used to estimate the event-free curves and corresponding quantiles (including the median). Data from subjects who have not received subsequent therapy will be censored at the earliest of death or the last time that lack of administration of a new therapy was objectively documented.

Protocol: ACE-LY-001

5.4.5 Analysis of Pharmacokinetic/Pharmacodynamic Parameters

The plasma pharmacokinetics of acalabrutinib and ACP-319 and a metabolite (M20) of ACP-319 will be characterized using noncompartmental analysis. The following PK parameters will be calculated, whenever possible, from plasma concentrations of analytes:

AUC $_{0\text{-last}}$ Area under the plasma concentration-time curve calculated using trapezoidal summation from time 0 to time last, where "last" is the time of the last measurable concentration (C_t)

AUC₀₋₁₂ Area under the plasma concentration-time curve from 0 to 12 hours, calculated using trapezoidal summation

AUC_{0-inf} Area under the plasma concentration-time curve from 0 to infinity, calculated using the formula: AUC_{0-inf} = AUC_{0-last} + C_{last} / λ_z , where λ_z is the apparent terminal elimination rate constant

AUC $_{0\text{-}24\text{calc}}$ Area under the plasma concentration-time curve from 0 to 24 hours, calculated by doubling the value for AUC $_{0\text{-}12}$

C_{max} Maximum observed plasma concentration

T_{max} Time of the maximum plasma concentration (obtained without interpolation)

t_{1/2} Terminal elimination half-life (whenever possible)

 λ_z Terminal elimination rate constant (whenever possible)

CL/F Oral clearance

[figure not shown]
Vz/F: Oral volume of distribution

Missing dates or times may be imputed for PK and PD samples if the missing values can be established with an acceptable level of accuracy based on other information obtained during the visit in question. Steady state predose drug concentrations may be used to estimate the subsequent trough (12 hour) concentration when 12-hour concentration data are not available. If PK and PD sampling for a given subject is not performed according to protocol instructions, that subject may be excluded from the PK and PD analyses.

The PK parameters will be tabulated and summarized using descriptive statistics.

Protocol: ACE-LY-001

For each PD variable, the concentration at each assessment will be described. The change from baseline to each assessment will be summarized. The best change from baseline during the study will also be summarized. As appropriate, the on-treatment values will be compared with the pretreatment baseline values using paired t-tests. P-values of ≤0.05 will be considered significant.

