2.2 SECONDARY OBJECTIVES

To document the extent of study drug exposure as determined by coadministration of acalabrutinib and ACP-319

To evaluate the PD effects of acalabrutinib and ACP-319 administration

To evaluate the activity of acalabrutinib and ACP-319 as measured by response rate, duration of response, progression-free survival, and time-to-next treatment

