MCL, characterized by documentation of monoclonal B cells that have a chromosome translocation t(11;14)(q13;q32) and/or overexpress cyclin D1 iNHL

- FL, Grade 1, 2, or 3a
- o WM
- o CLL/SLL

Multiple myeloma (MM)

B-cell acute lymphoblastic leukemia (B-ALL)

Note: Under Amendment 4 of this protocol, enrollment in Part 2 is closed for all cohorts except the non-GCB DLBCL cohort.

Note: Under Amendment 6 of this protocol, all active subjects will receive acalabrutinib monotherapy (100 mg BID).

Treatment with acalabrutinib (and previously ACP-319), in Part 1 and Part 2, may be continued until disease progression or an unacceptable drug-related toxicity occurs as defined in the protocol. Dose modification provisions are provided in the study protocol. Note: Temporary withholding of study drug for as little as 7 days can cause a transient worsening of disease and/or of constitutional symptoms. Refer to Section 3.12 for more information on assessing disease progression under these circumstances. All subjects who discontinue study treatment will have a safety follow-up (SFU) visit 30 (+ 7) days after the last dose of study drug and will be followed every 3 months thereafter until disease progression or the start of alternative anticancer treatment.

All subjects will have hematology, chemistry, and urinalysis safety panels performed at screening. Once dosing commences (Day 1), all subjects receiving acalabrutinib (and previously ACP-319) combination therapy will be evaluated for safety, including serum chemistry and hematology, on Cycle 1 Days 1, 8, 15, 22, and 28, Cycle 2 Days 15 and 28, then monthly through Cycle 24, and every 3 months thereafter. ECGs will be obtained at screening, repeatedly during Cycle 1, at each study visit through Cycle 6, and at each study visit in Cycles 9 and 12. PK testing will be done in Cycles 1 to 4. PD testing will be done in Cycles 1 and 2, and at the treatment termination (TT) visit. Radiologic tumor assessments will be done at screening and at the end of Cycle 2, Cycle 4, and Cycle 6; every 3 cycles (12 weeks) through Cycle 18, and then every 6 cycles thereafter, or more frequently at the investigator's discretion.

[figure not shown]
Protocol: ACE-LY-001

Refer to Appendix 5 for a comprehensive list of study assessments and their timing (acalabrutinib monotherapy).

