4.1.20 Pharmacodynamics and Correlative Studies

Blood samples will be used for PD testing (e.g., BTK occupancy and B-cell activation), cytokine analysis, and for further characterization of circulating lymphocyte and myeloid cell subsets.

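### Section 5.4.5 calls pharmacodynamic p-values of 0.05 or less significant without limiting the number of tests, adjusting for them or labelling them nominal

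*Protocol*

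**What the plan says.** Protocol Section 2.2 lists as a secondary objective: "To evaluate the PD effects of acalabrutinib and ACP-319 administration".

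Section 5.4.5 sets out the analysis in four steps. The first is descriptive and covers all variables: "For each PD variable, the concentration at each assessment will be described". Changes from baseline to each assessment are then summarized, and for best change the text says: "The best change from baseline during the study will also be summarized". The tests follow: "As appropriate, the on-treatment values will be compared with the pretreatment baseline values using paired t-tests". The paragraph closes with the rule at issue: "P-values of ≤0.05 will be considered significant". No other section of the protocol sets a significance threshold for the trial's own analyses; response rate is given with a confidence interval and the time-to-event endpoints with Kaplan-Meier estimates.

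Three other places bear on how many tests there could be:
- **Variables.** Section 4.1.20 says blood samples serve for "PD testing (e.g., BTK occupancy and B-cell activation), cytokine analysis" and for characterizing circulating lymphocyte and myeloid subsets. The two named PD measures are examples, not a closed list.
- **Times.** Section 3.0: "PD testing will be done in Cycles 1 and 2, and at the treatment termination (TT) visit". The number of samples within each cycle is not given there.
- **Groups.** Section 5.1: "analyses will be performed by dosing cohort, cancer type, or overall", again only where appropriate.

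**The concern.** The protocol is not merely silent on multiplicity, which could be left to the SAP. It fixes a rule for what may be called significant and attaches it to a set of tests that is never closed. An SAP that declared these p-values nominal would contradict the protocol sentence, so the sentence has to change where it stands.

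At stake is what may be claimed about a secondary objective. Section 5.1 also justifies six subjects per cohort partly by the wish to explore dose-dependent effects on PD biomarkers, so these results will be looked at. A chance change in one marker at one visit could be reported as a significant PD effect, although the error rate across the set of tests is well above the 5% that the word suggests.

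**Working it through.** **Inputs from the protocol**
- Threshold per test: p ≤0.05 (Section 5.4.5). Sidedness is not stated; two-sided is assumed.
- Test: paired t-test against baseline (Section 5.4.5).
- Group sizes: 6 per Part 1 cohort and up to 12 per Part 2 histology (Section 3.0); 18 is the Part 1 total.

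**Inputs that must be assumed**
- Number of tests, m. A narrow count is 2 variables (the two named examples) × 2 times (Cycles 1 and 2, one assessment each) = 4. A broader count is 4 variables (adding cytokines and cell subsets, one each) × 3 times (adding treatment termination) = 12. Both are for one analysis group only.
- Correlation between tests, ρ: 0, 0.5 and 0.8.

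**Step 1: a single test.** The 0.05 threshold is a chosen constant, so there is no derived figure to reproduce. Simulated paired t-tests with no true change reject in about 5% of runs (0.046 to 0.055) at n = 6, 12 and 18. One test is therefore sound at its nominal level.

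**Step 2: independent tests.** The chance of at least one p ≤0.05 under no change is 1 − (1 − 0.05)^m.
- m = 4: 1 − 0.95⁴ = 0.185
- m = 6: 1 − 0.95⁶ = 0.265
- m = 8: 1 − 0.95⁸ = 0.337
- m = 12: 1 − 0.95¹² = 0.460

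The expected number of false positives is 0.05m, so 0.2 for 4 tests and 0.6 for 12, whatever the correlation.

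**Step 3: correlated tests.** For each subject, the change on each test was simulated as √ρ × (a shared normal term) + √(1 − ρ) × (a separate normal term), with mean zero. Each test used t = mean / (SD/√n) on n − 1 degrees of freedom. There were 4,000 runs per setting, so the Monte Carlo standard error is about 0.005 to 0.008.

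| m | n | ρ = 0 | ρ = 0.5 | ρ = 0.8 |
|---|---|---|---|---|
| 4 | 6 | 0.194 | 0.168 | 0.122 |
| 4 | 12 | 0.188 | 0.160 | 0.118 |
| 12 | 6 | 0.467 | 0.354 | 0.214 |
| 12 | 12 | 0.448 | 0.337 | 0.202 |

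The ρ = 0 column agrees with the formula within simulation error, and group size matters little. Taking the exact values at ρ = 0 and the simulated ones at ρ = 0.8, the range is about 12-19% for 4 tests and 20-46% for 12.

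**The case against.** The strongest reply is that this is a single-arm proof-of-concept study with safety as its primary objective and a generally descriptive analysis. Escalation rests on dose-limiting toxicities, and expansion on the safety and efficacy results of Part 1. No decision uses a PD p-value, and listing the PD tests and their handling is normal SAP material. The point about decisions stands in full and sets the severity. The point about the SAP stands for the list of tests, but not for the significance label, which the protocol itself has fixed.

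Three stronger readings are tempting and are not supported:
- *Every variable, visit and subgroup is tested.* Both the t-tests and the grouping are qualified as done where appropriate. Only the descriptive summaries cover each variable at each assessment.
- *A false positive is likely.* With independent tests, a chance above one half needs 14 or more (ln 0.5 / ln 0.95 = 13.5), and more if they are correlated. The protocol does not give the number.
- *Best change is t-tested.* Section 5.4.5 says only that it is summarized; the t-test sentence refers to on-treatment values.

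The broader count of 12 is also open to challenge. Cytokines and cell subsets may be meant as correlative rather than PD variables, and the treatment termination visit follows permanent discontinuation, so it may not count as on-treatment. The table of contents lists a Section 5.4.6 on explorative or correlative analyses whose text is not in the copy reviewed; nothing is inferred from that. These doubts are why 4 tests is shown alongside 12.

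**Conclusion.** The point holds in a limited form. Section 5.4.5 applies an unadjusted significance label to an open-ended set of PD tests on a secondary objective. The qualifier on testing does not cure this, because it leaves the choice of tests open while the label stays fixed. If there is no true change, the chance of at least one result wrongly called significant is about 12-19% with 4 tests and 20-46% with 12, roughly 2 to 9 times the nominal 5% (12/5 = 2.4; 46/5 = 9.2).

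These figures rest on assumed numbers of tests, equal correlations between 0 and 0.8, two-sided testing and normally distributed changes. The severity is low, because no decision rule in the protocol rests on these p-values. The harm is confined to how PD findings may be described.

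**What to change.** In Section 5.4.5, replace "P-values of ≤0.05 will be considered significant" with: *Changes from baseline will be reported with two-sided 95% CIs; PD p-values are nominal, unadjusted for multiplicity, and will not be described as statistically significant; best change from baseline will be summarized descriptively only.*

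The last clause settles a point that the present wording leaves to inference. A formal adjustment would first need a closed list of variables, times and groups, which the protocol does not have; the nominal label needs none.

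The cost is one sentence in the protocol and matching wording in the SAP, with no new data and no change to sampling. The small downside is that unadjusted PD p-values can no longer be called significant.

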6.0 ASSESSMENT OF SAFETY

Safety assessments will consist of monitoring and recording AEs and SAEs; measurements of protocol-specified hematology, clinical chemistry, urinalysis, and other laboratory variables; measurement of protocol-specified vital signs; and other protocol-specified tests that are deemed critical to the safety evaluation of the study drug(s).

6.1 REFERENCE SAFETY INFORMATION

For the purpose of reporting AEs and SAEs, the Investigator Brochure for acalabrutinib contains the Reference Safety Information (RSI).

6.2 **DEFINITIONS**

6.2.1 Adverse Events

An AE is any unfavorable and unintended sign, symptom, or disease temporally associated with the use of an investigational (medicinal) product regardless of attribution.

This includes the following:

AEs not previously observed in the subject that emerge during the protocol-specified AE reporting period, including signs or symptoms associated with the primary hematologic malignancy that were not present before the AE reporting period (see Section 6.3.1).

Protocol: ACE-LY-001

Preexisting medical conditions (other than the condition being studied) judged by the investigator to have worsened in severity or frequency or changed in character during the protocol-specified AE reporting period.

Abnormal laboratory values considered clinically significant by the investigator should be reported as AEs.

The following are NOT considered an AE:

Pre-existing condition that has not worsened: A pre-existing condition (documented on the medical history CRF) is not considered an AE unless the severity, frequency, or character of the event worsens during the study period.

Preplanned hospitalization: A hospitalization planned before signing the ICF is not considered an SAE, but rather a therapeutic intervention. However, if during the preplanned hospitalization an event occurs, which prolongs the hospitalization or meets any other SAE criteria, the event will be considered an SAE. Surgeries or interventions that were under consideration, but not performed before signing the ICF, will not be considered serious if they are performed after signing the ICF for a condition that has not changed from its baseline level. Elective hospitalizations for social reasons, solely for the administration of chemotherapy, or due to long travel distances are also not SAEs.

Diagnostic testing and procedures: Testing and procedures should not be reported as AEs or SAEs but rather the cause for the test or procedure should be reported. If a test or procedure is done to rule out a diagnosis, the sign or symptom leading to the test/procedure should be the event term, and the event term should only be updated to the diagnosis if/when the diagnosis is confirmed. Testing and procedures performed solely as screening measures (e.g., routine screening mammography or colonoscopy) should not be reported as AEs or SAEs.

Abnormal laboratory results that the investigator considers to not be clinically significant: Abnormal laboratory results are not AEs unless they are clinically significant. For example, a clinically significant laboratory result is one that requires treatment (for example a blood transfusion for low hemoglobin) or requires a change in study drug (e.g., lowering the dose or withholding study drug while the laboratory finding resolves or stabilizes).

